eGFR	Estimated glomerular filtration rate
EMA	European Medicine Agency
FEP	Full eligible population
FIP	Full included population
GBCA	Gadolinium-based contrast agents
GBCAP	Population by GBCA type
GFRP	Population by GFR rate
HISALP	Population by history of allergy
MR	Magnetic resonance
MRA	Magnetic resonance angiography
MRI	Magnetic resonance imaging
PET	Positron-emission tomography
PT	Preferred Term
SAF	Safety population
SAP	Statistical Analysis Plan
SAS	Statistical Analysis System
SOC	System Organ Class
SPECT	Single photon emission computed tomography
SPP	Population by specialty

1 INTRODUCTION

1.1 Rationale for study

It is currently unknown and of high scientific interest with which dosages the radiologists use the gadolinium-containing contrast media currently available in their market. Such information, which is very important for the referring physicians, can only be obtained by up-to-date observation and documentation in the daily routine.

It is also currently unknown and of further interest for the assessment of the applications, which criteria referrers consider for the administration of gadolinium-containing contrast agents after the publication of the EMA/457616/2017 requirements. In particular, it is unknown whether the presence of pre-existing renal insufficiency is taken into consideration, how often MR contrast agents are used in the same patient and whether this is dependent on indication and/or comorbidities. For example, this question is relevant to patients evaluated for multiple sclerosis and cancers, where it is unknown if notwithstanding the known brain retention of gadolinium, repeated contrast enhanced MR scans are considered necessary. Also, it is unknown if dose reductions, perhaps dependent on scanner magnetic field strength, are applied.

The study plan/protocol and the resulting documentation sheet of the requested study accurately collects data useful to clarify these points and will therefore provide more accurate insight into the potentially adapted clinical procedure.

1.2 Purpose of the analyses

The study is set-up for descriptive purposes, no a priori hypothesis will be tested.

The statistical analysis plan (SAP) is a more detailed description of the statistical rationale and the methods used for generating the results of this observational study.

It contains additional information not covered by the study protocol (Version 1.5, 28-Nov-2018).

2 STUDY OBJECTIVES AND ENDPOINTS

2.1 Study objectives

Primary objectives:

The primary objective of the GBCA observational study, will be to prospectively collect data on the pattern of use for GBCA in real-life setting with special reference to Clariscan after its commercial launch in Europe.

Secondary objectives:

The study will look at the effectiveness and safety profile of GBCAs including Clariscan in clinical practice

3 STUDY METHODS

3.1 Study design and plan description

This is a prospective, multi-center observational study.

It is planned to enroll up to 5400 patients from 7 countries and 14 sites.

3.2 Study variables

3.2.1 Patient data

3.2.1.1 Signed informed consent

- Yes/Date
- No

3.2.1.2 Demographics and baseline characteristics

- Age
 - Child: birth – 4 weeks, 5 weeks – 6 month, 7 month – 12 month. 13 month – 2 years, 3 years – 4 years, 5 years - 9 years, 10 years to 18 years; Adult: 19 Years to 89 years, > 89 years; for adults aged 19-89 years the exact age will be documented)
 - Pediatric:0-18 years, non-elderly adults: 19 to 59 years, elderly adults: ≥60 years

- Gender (male/female)
- Pregnancy status (yes, no, not applicable)
 - If applicable weeks of pregnancy (on day of visit)
- Weight (kg)
- Height (m)
- BMI will be derived from weight and height via $BMI = \text{weight (kg)} / \text{height(m)}^2$

3.2.1.3 Medical summary

- Diagnosis to which MR scan has been indicated
- Question to be answered with the use of CE-MR
- Secondary diagnosis
- Reason for using a contrast medium (border delineation of pathology, overall morphological characterization of pathology/lesion, overall increase in resolution of images required, confirmation of opinion/diagnosis, for comparison with non-contrast enhanced images, angiography or myocardial assessment, standard procedure for this diagnostic question, other)
- Specific reason why the GBCA was used
- Comorbidities (none, allergy, diabetes mellitus, heart failure, hepatic impairment, hypertension, neurologic symptom, renal impairment, autoimmune disease, malignancy/cancer, other)
 - Allergy status for patients with allergies (bronchial asthma, eczema, food allergy, urticaria, previous history of allergy to other contrast media [unknown media, Iodine-based media, Gadolinium-based media, ultrasound media, other media])
 - Renal status eGFR for patients with renal impairment (< 15, 15-30, 31-60, > 60 mL/min/m², impaired [exact eGFR unknown], unimpaired [exact eGFR n/a])
 - If renal status < 60 mL/min/m²: status of renal replacement for the compromised kidney(s) (renal replacement – dialysis, renal transplant, no replacement)
- Pre-medications (none, steroids, anti-histamines, other)
- Concomitant medications (no co-medication, chemotherapy/active treatment for malignancy, radiotherapy, anti-hypertensives, diabetic medications, heart failure treatment, nephrotoxic medication [antibiotics, iodinated agents, oncological drugs, immunosuppressants, other], other)
- Source of funding for the scan (self-funded [n/a, full, partially], paid by personal/hospital insurance, reimbursed by the state)

- If funding = insurance or reimbursed, what is being paid for (contrast media, procedure, procedure including contrast media)

3.2.1.4 Referral details

- Quality of referral notes (not enough information, satisfactory levels of information, detailed information with clear medication)
- Referral type (routine, emergency, follow-up, repeat scan identical to previous scan)
 - If repeat scan, reason for repeat scan (poor quality image [patient-related factors, contrast-related factors, imaging-technique related factors], other)
- Referring physician seniority (resident, registrar or equivalent; consultant or equivalent; consultant with a specialist interest in the field)
- Referring physician specialty (cardiology, gastroenterology, gynecology, internal medicine, neurology, oncology, orthopedics, respiratory medicine, rheumatology, urology, other)

3.2.1.5 MR Examination

- Organ/system under examination (brain/meninges/spinal cord, head and neck, breast, bronchial tissue/lungs, cardiovascular, renal, hepatobiliary, pancreas, gastrointestinal tract, urinary tract incl. bladder, genital tract incl. gonads, endocrine glands, musculoskeletal system incl. bones/joints/muscles, lymphoid tissue incl. blood disorders, whole body, other)
- Indication (CNS indication [brain/meninges/spinal cord], organ/whole body [all other organs (if not MRA like a cardiovascular MRA)], angiography [any MRA])
- MRI details (if applicable)
 - Brand of contrast agent
 - Volume of contrast agent (ml)
 - Injector use (yes/no)
 - Volume of saline follow-up injection (none or in mL)
 - Scanner make (GE, Siemens, Philips, other)
 - Field strength (1.5T, 3T, >3T)
 - Scanner model
 - Scan modality (dynamic, delayed, both dynamic and delayed)

- Type of sequence/protocol (standard, modified)
 - If modified, reason for modifying the sequence (improvement of image quality, removal of artifacts preventing a diagnostic image, patient related reason, other)
- MRA details (if applicable)
 - Brand of contrast agent
 - Volume of contrast agent (ml)
 - Injector use (yes/no)
 - Volume of saline follow-up injection (none or in mL)
 - Scanner make (GE, Siemens, Philips, other)
 - Field strength (1.5T, 3T, >3T)
 - Scanner model
 - Scan modality (dynamic, delayed, both dynamic and delayed)
 - Type of sequence/protocol (standard, modified)
 - If modified, reason for modifying the sequence (improvement of image quality, removal of artifacts preventing a diagnostic image, patient related reason, other)
- MRA or MRI part of a broader pathway to clarify the illness under investigation (yes, no)
- Any other image scan before the MR scan in relation to the illness under investigation (none, CT, ultrasound, CE-MR, liver-specific MR, non-CE-MR, SPECT, PET, X-ray (excluding CT), other)

3.2.1.6 Diagnosis after MRI

- Did contrast enhanced MRI change radiological diagnosis (yes, no)
- Did contrast enhanced MRI increase the radiologist's confidence in diagnosis compared to non-contrast enhanced MRI (yes, no)
- Radiologist's confidence in diagnosis at the time of referral, before CE-MRI (visual analogue scale 0-100%)
- Radiologist's confidence in diagnosis at the time of referral, after CE-MRI (visual analogue scale 0-100%)
- Quality of CE-MRI image (poor/inadequate, fair/partial, good/adequate, excellent)

3.2.1.7 Diagnosis after MRA

- Did contrast enhanced MRA change radiological diagnosis (yes, no)
- Did contrast enhanced MRA increase the radiologist's confidence in diagnosis compared to non-contrast enhanced MRA (yes, no)
- Radiologist's confidence in diagnosis at the time of referral, before CE-MRA (visual analogue scale 0-100%)
- Radiologist's confidence in diagnosis at the time of referral, after CE-MRA (visual analogue scale 0-100%)
- Quality of CE-MRI image (poor quality & blurred arterial segment, fair/inadequate for confident diagnosis, good/adequate for confident diagnosis, excellent/adequate for highly confident diagnosis)

3.2.1.8 Adverse Events

- Adverse Event (AE) verbatim
- Serious AE (yes, no)
- Date/time of onset
- Date time of ending
- Causality (not related, possibly related, probably related, definitely related)
- Onset of AE (immediate [up to 1-hour post-injection], delayed [between 1 h and 7 days post-injection])
- Severity of AE (mild/tolerable, moderate/interferes with normal activity, severe/incapacitating)

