5.2 Timing of analyses

An interim analysis of the data sampled until mid of February 2019 is planned.

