5.4 Handling of dropouts

Not applicable

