6 ANALYSIS SETS

The allocation of subjects to analysis sets will be determined by the sponsor and the CRO on a per-subject basis immediately before data base lock.

Full eligible population (FEP)

The FEP population consists of all screened subjects, both successful and failed screens.

Full included population (FIP)

The FIP population consists of all successful screens.

Safety population (SAF)

The SAF population consists of all patients with a documented MRI/MRA procedure.

Population by country/site (CSP)

The CSP population consists of all successful screens in with known country/site.

Population by GBCA type (GBCAP)

The GBCA population consists of all subjects with known GBCA brand type.

Population by speciality (SPP)

The SPP population consists of all subjects examined for an ailment with known speciality.

Population by GFR rate (GFRP)

The GFR population consists of all subjects with known range of GFR rate.

Population by History of allergy (HISALP)

The history of allergy population consists of all subjects with known history of allergy status.

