7 STATISTICAL METHODS

All continuous variables will be summarized using the following descriptive statistics: n (non-missing sample size), mean, standard deviation, median, minimum and maximum. The frequency and percentages (based on the non-missing sample size) will be reported for categorical measures. Data that will be listed will be sorted by country, site and subject.

For the comparison of endpoints in stratified analyses (e.g. by country, by GBCA etc.) explorative statistical tests will be applied (ANOVA for continuous endpoints, Chi-Square tests for categorical endpoints) if feasible.

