7.3 Adverse events

Analysis of safety will be based on the safety population (SAF).

The number and frequency of patients with adverse events and serious adverse events will be analysed overall, by age group (SAF), by history of allergy (HISALP), by GFR rate (GFRP), by site (CSP) by country (CSP), by specialty (SPP) and by GBCA (GBCAP) by MedDRA SOC and PT.

The number and frequency of adverse events will also be analysed for the subgroups given above stratified by causality, treatment, severity and onset of the adverse event.

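### The SAP's delayed-AE percentages take no account of its own 7-day window, so recent scans at the interim, and any patient without 7-day information, stay in the denominator (minor)

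*SAP*

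**What the plan says.** - **Window.** Section 3.2.1.8 splits AEs by timing: "Onset of AE (immediate [up to 1-hour post-injection], delayed [between 1 h and 7 days post-injection".
- **Denominator.** Section 7.3 states: "Analysis of safety will be based on the safety population (SAF". Section 6 defines that set: "The SAF population consists of all patients with a documented MRI/MRA procedure". The sets used for breakdowns by country or site, GBCA, specialty, GFR and allergy history are defined by a known value of the grouping variable. None has a follow-up condition.
- **Use of onset.** Section 7.3 has AE frequencies "stratified by causality, treatment, severity and onset of the adverse event". Appendix 1 lists time-to-onset tables overall and by site, country, specialty and GBCA (Tables 11.1.6, 11.2.6, 11.3.6, 11.4.6 and 11.5.6).
- **Percentage base.** The general rule in section 7 is: "The frequency and percentages (based on the non-missing sample size) will be reported for categorical measures".
- **Incomplete follow-up.** Under "5.4 Handling of dropouts" the whole entry is "Not applicable". Section 5.5 says that missing values are not replaced.
- **Interim.** Section 5.2 reads, in full: "An interim analysis of the data sampled until mid of February 2019 is planned".

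**The concern.** An outcome that takes up to 7 days to observe can be unknown for some patients at any data cut. The SAP defines such an outcome, but its denominators, its dropout entry and its interim rule read as if every patient's AE status were complete at the scan. A patient whose window is still open, or about whom nothing is known after the scan, contributes to the denominator and normally nothing to the numerator.

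The safety profile of GBCAs is part of the secondary objective (section 2.1). Section 7 also allows exploratory chi-square tests between strata, with 0.05 as the threshold (section 5.8) and no adjustment for multiplicity (section 5.7). If completeness of 7-day information differs between sites, and brand goes with site, a difference in completeness could be read as a difference between contrast agents.

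**Working it through.** The SAP gives no AE rate and no calculated sample size, so there is no figure to reproduce. The check has three parts.

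**1. Interim cut: follows from the SAP if delayed AEs are tabulated then.**
Inputs: window of 7 days (section 3.2.1.8); cut at mid-February 2019 with no minimum follow-up (section 5.2). Assumption: uniform accrual over D days before the cut. D is not given, so a range is shown.

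- Share of patients with an open window = 7/D.
- A patient injected t days before the cut (t < 7) has lost (7 − t)/7 of the window. Averaged over t from 0 to 7 this is 1/2, so the share of total window time lost = (7/D) × 1/2 = 3.5/D.

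| D (days) | Open window, 7/D | Window time lost, 3.5/D |
|---|---|---|
| 30 | 23.3% | 11.7% |
| 60 | 11.7% | 5.8% |
| 90 | 7.8% | 3.9% |
| 180 | 3.9% | 1.9% |

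The second column of percentages is closer to the effect on the rate. It equals the expected share of delayed AEs missed only if onset is spread evenly over the 7 days; if onset is concentrated early, less is lost.

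**2. Patients without 7-day information: direction clear, size not computable.**
Let f be the share of patients with known 7-day status and p the true delayed-AE risk. If patients outside f report nothing, the expected rate over all scanned patients is f × p, a relative shortfall of 1 − f. Neither f nor p is in the SAP. Over an assumed range, f = 1.0, 0.9, 0.5 and 0.3 give shortfalls of 0%, 10%, 50% and 70%. These are upper limits for each f, because some patients who are not followed may still report an event. If two groups share a risk of 1% (assumed) but have f = 0.9 and f = 0.5 (assumed), the expected rates are 0.9% and 0.5%.

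The non-missing rule in section 7 does not settle the denominator. The AE items in section 3.2.1.8 describe an event that has occurred. Applied literally to the onset item, the rule gives percentages among patients with an AE. It would separate patients followed without an AE from patients not followed only if a 7-day status were recorded, and section 3.2 lists none.

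**3. What a corrected denominator must avoid.**
Suppose N = 5400 (the planned maximum, section 3.1), a true risk of 1%, 10% of patients actively followed, and every event in the rest self-reported (the last three are assumptions). Events: 5400 × 0.01 = 54, of which 5.4 are among the 540 followed and 48.6 among the others.

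- Over all scanned patients: 54/5400 = 1.0%, correct here.
- Over patients with any information, counting a self-report as information: 54/(540 + 48.6) = 9.2%, badly inflated.
- Over patients whose follow-up was completed irrespective of AE reporting, counting only their events: 5.4/540 = 1.0%.

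So completion must be defined independently of whether an AE was reported, and the numerator must be restricted to the same patients.

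**The case against.** The strongest reply is that ascertainment to day 7 belongs to the protocol, which is not shown. A delayed category with onset and end times implies that some later information is intended. If each record is closed only after a day-7 contact, part 2 of the working shrinks towards nothing, and the dropout entry is unremarkable for the final analysis. Nor does silence in section 3.2 prove that no follow-up status is collected, since the list is not exhaustive: section 7.3 uses treatment of the AE and section 7.2.2 uses reasons for satisfaction ratings, and neither is listed there. All exposed patients is also the conventional safety denominator, the study is descriptive, and section 5.2 does not say that delayed AEs will be in the interim output.

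Most of this stands. A reader might infer that many patients are lost after the scan and that the delayed-AE rates are therefore biased downward by a large amount. The SAP does not support that: it says nothing about how many patients lack 7-day information.

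Two things remain whatever the protocol says. A calendar cut without a window rule leaves recently injected patients with open windows, however well later follow-up is done. And the denominator, the dropout entry and the interim rule are SAP content; as written, they do not refer to the SAP's own 7-day window.

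**Conclusion.** The point holds in a limited form, as a minor one. At the interim, if delayed-AE percentages are produced, 7/D of patients are counted with an incomplete window and about 3.5/D of window time is missing. Under uniform accrual that is 23% and 12% at D = 30, falling to 4% and 2% at D = 180, so it matters only if accrual before the cut was short. Beyond the interim, any patient without 7-day information is counted as free of delayed AEs unless an event happens to be reported. The direction is downward, but its size cannot be derived from the SAP and depends on the protocol's follow-up procedure. A demonstrated downward bias in the final rates, or a spurious difference between brands, would be a stronger conclusion than the document allows.

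**What to change.** 1. **Section 5.2:** limit interim delayed-AE percentages to patients injected at least 7 days before the cut.
2. **Section 7.3:** report immediate AEs over SAF. Report delayed AEs as counts over SAF, together with the number of patients, by site and GBCA, whose 7-day follow-up was completed. Define completion independently of whether an AE was reported. Give delayed-AE percentages only among those patients, counting only their AEs in the numerator.
3. **If completion is not recorded:** report delayed AEs as counts of reported events, without tests between GBCAs or between sites.
4. **Section 5.4:** replace the present entry with a statement of how patients without completed 7-day follow-up are handled, consistent with the above.

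**Cost.** Items 1, 3 and 4 are mainly SAP wording; item 1 also needs an injection or scan date in the dataset. Item 2 is wording if completion is already captured. If it is not, a new field is a change to data collection shortly before the interim (the SAP is dated 22 January 2019, the cut is mid-February 2019), and item 3 is the way to avoid it. The price is a smaller denominator and a less favourable delayed-AE rate.

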3.2.2 Investigator data

- Date of first patient
- Date of last patient
- Total number of patients visited by this investigator during the study period
- Number of procedures performed by the investigator (liver-specific MR, Non-CE MR, CE-MRI, CE-MRA, CT, ultrasound, PET-PET/CT-PET/MR, SPECT, X-ray, other)

3.2.3 Centre data

- Number of available scanners in centre (MRI, CT, ultrasound, PET-PET/CT, PET/MR, SPECT, X-ray)
- Number of procedures performed in the centre (liver-specific MR, Non_CE MR, CE-MRI, CE-MRA, CT, ultrasound, PET-PET/CT-PET/MR, SPECT, X-ray, other) during the study period
- Number of staff members (radiologists, radiographers, nurses)
- Decision for use of a specific contrast medium (individual decision, collective decision)
- Decision maker for use of specific contrast medium (Head of radiology department, radiologist, specialty physician, pharmacist, manager [non-clinician], other)
- Challenges faced by radiology department
- User satisfaction with GBCA packaging and injectors
 - for each GBCA
 - Satisfaction with GBCA packaging (could be improved, o.k., excellent/particularly good)
 - Satisfaction with injector (could be improved, o.k., excellent/particularly good)

4 SAMPLE SIZE CALCULATION

The sample size is not based on statistical considerations, as the study does not formally test a hypothesis.

5 GENERAL STATISTICAL CONSIDERATIONS

5.1 General principles

Analysis will be performed using SAS software package release Version 9.4.

5.2 Timing of analyses

An interim analysis of the data sampled until mid of February 2019 is planned.

5.3 Covariates and subgroups

Endpoints will additionally be stratified by site, specialty, country, GBCA type, scanner type, scanner field strength, scan modality where applicable

5.4 Handling of dropouts

Not applicable

5.5 Handling of missing data

All analyses will be performed without replacing missing values.

5.6 Multi-center studies

Not applicable

5.7 Multiple testing

Due to the explorative design of the observational study there will be no adjustments for multiple statistical tests.

5.8 Statistical significance (p-values)

A p-value of <0.05 will be declared as statistically significant.

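### Section 5.8 labels any p<0.05 statistically significant in an exploratory, unadjusted study with no planned confidence intervals, so false significant findings are likely

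*SAP*

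**What the plan says.** SAP section 1.2 states the purpose: "The study is set-up for descriptive purposes, no a priori hypothesis will be tested". Section 4 gives the absence of a formal hypothesis test as the reason why the sample size has no statistical basis.

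Section 7 nevertheless plans tests: "For the comparison of endpoints in stratified analyses (e.g. by country, by GBCA etc.) explorative statistical tests will be applied". The methods and their condition are "ANOVA for continuous endpoints, Chi-Square tests for categorical endpoints) if feasible". Section 5.3 names seven stratifiers: "Endpoints will additionally be stratified by site, specialty, country, GBCA type, scanner type, scanner field strength, scan modality where applicable".

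On multiplicity, section 5.7 says: "Due to the explorative design of the observational study there will be no adjustments for multiple statistical tests". Section 5.8 then consists of one sentence: "A p-value of <0.05 will be declared as statistically significant".

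For continuous variables, section 7 lists "n (non-missing sample size), mean, standard deviation, median, minimum and maximum". Categorical variables get frequencies and percentages. Section 9 sets a format for p-values. Sections 5, 7 and 9 and Appendix 1 do not mention a confidence interval.

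**The concern.** Exploratory p-values without adjustment are acceptable when they are read as exploratory. A standing rule that every result below 0.05 is declared significant gives them a status that the rest of the SAP disclaims. Section 5.8 has no qualifier of its own, so a table or report written to it would print the label without the caveat.

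The primary objective in section 2.1 makes special reference to one brand. An unadjusted significant difference between GBCAs, in image quality or AE frequency for example, could be taken up as a comparative claim that the study was not set up to support.

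The quantities that the study exists to describe (dose, patterns of use, AE rates) would be reported without a stated precision. For rare AEs that omission matters more than any p-value.

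**Working it through.** The SAP gives no error rate or power to reproduce. The check therefore counts the opportunities for a false significant result and shows what intervals would add.

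**Number of stratified tables (Appendix 1).** There are 99 tables, of which 79 are split by a factor: 52 non-AE tables and the 27 AE tables in 11.2.1 to 11.6.3. Leaving out disposition and observation period (1.2, 1.3, 2.2), two within-topic cross-tabulations (6.1.4, 7.11) and the AE summary by severity (11.6.1) gives 79 − 6 = 73. These are 47 non-AE and 26 AE tables.

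**Formulas.** With m independent tests at 0.05 and no true differences, the expected number of false positives is 0.05 × m, and P(at least one) = 1 − 0.95^m.

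| Set of tables, one test each | m | Expected | P(at least one) |
|---|---|---|---|
| All stratified endpoint tables | 73 | 3.65 | 0.976 |
| Without the 26 AE tables | 47 | 2.35 | 0.91 |
| GBCA (12) and country (9), non-AE | 21 | 1.05 | 0.66 |
| The same plus AE blocks 11.3 and 11.5 (12) | 33 | 1.65 | 0.82 |

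The last row treats 11.3 as the country block and 11.5 as the GBCA block. Their first tables (11.3.1, 11.5.1) are titled by site, but the other tables in each block show the intended factor.

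**Correlation.** For equicorrelated two-sided z-tests with m = 73, P(at least one) is 0.89 at rho 0.3, 0.71 at rho 0.5 and 0.33 at rho 0.8. With m = 33 and rho 0.5 it is 0.53. Correlation leaves the expected counts unchanged.

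**More than one test per table.** Section 7.1.7 names six endpoints (contrast volume, saline volume, dose, injector use, sequence type, reason for modification), and Tables 7.2 to 7.8 split them seven ways. That is 6 × 7 = 42 possible tests, with 42 × 0.05 = 2.1 expected and 1 − 0.95^42 = 0.88. If all 73 tables carried two tests each (assumption), m = 146 gives 7.3 expected and P = 0.9994.

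**What intervals would show.** For a proportion of 50%, the 95% half-width is 1.96 × √(0.25/n). Section 3.1 gives up to 5400 patients, 7 countries and 14 sites. An equal split is assumed:
- overall, n = 5400: 1.3 points
- per country, n = 5400/7 = 771: 3.5 points
- per site, n = 5400/14 = 386: 5.0 points

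For an AE seen in 0 of 5400 patients, the two-sided 95% Clopper-Pearson upper limit is 1 − 0.025^(1/5400) = 0.068%. The rule of three, 3/5400 = 0.056%, is a one-sided 95% bound and should not be quoted as the limit of that interval.

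**The case against.** The strongest reply is that the SAP already calls these tests exploratory. Section 1.2 rules out only an a priori hypothesis, section 4 only a formal test, and sections 5.7 and 7 use the exploratory label. On that reading, 5.8 merely sets a nominal threshold for tests whose status is clear. This stands in part: there is no flat contradiction, and waiving adjustment is defensible. But nothing in 5.8 carries the qualifier into the tables, and declaring significance is a conclusion, not a descriptive summary.

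A second reply is that the SAP does not commit to 73 tests. Tests apply only where feasible, strata only where applicable, and Appendix 1 does not say which tables carry p-values. Chi-square tests will often be infeasible in the sparse AE tables by SOC and PT. Independence is also unrealistic, because sites sit within countries and the same AEs are tabulated repeatedly. All of this stands, and it is why the figures are given as a range.

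A reader might infer that false GBCA and country differences are certain. The documents do not support that. At one test per table the chance for those tables is 0.66 to 0.82 even with independent tests, and it approaches 1 only if tables hold several tests, a number the SAP leaves open. Real differences in practice between countries or brands are also plausible; finding those, even small ones in a large sample, is not a false positive.

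A reader might also infer that the output would contain no information on precision. That goes too far: n, SD and percentages allow a reader to derive a simple interval. What is missing is a planned and printed one.

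Section 5.6 plans nothing for the multi-centre structure, and ordinary tests ignore clustering by site. The per-test error could therefore exceed 5%, but no intracluster correlation is given, so the excess cannot be sized and is not counted here.

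**Conclusion.** The point holds as a mismatch of status plus an omission. An unqualified significance rule sits in a plan that calls its tests exploratory and unadjusted, and no confidence interval is planned for dose, usage proportions or AE rates. With one test in each of 73 tables, about 3.7 false significant results would be expected if no true differences existed. The chance of at least one is 0.98 under independence and 0.71 at a correlation of 0.5. These figures rest on that assumed number of tests, so false significant findings are likely, not certain. The correction is cheap and changes what a reader may conclude from the output, especially about differences between GBCAs.

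**What to change.** - **Section 5.8:** replace the sentence with a statement that all p-values are nominal, unadjusted for multiplicity and exploratory, and that they will not be declared statistically significant or used for comparative claims between GBCAs.
- **Section 7:** add 95% confidence intervals for mean dose and the main proportions, and exact (Clopper-Pearson) 95% confidence intervals for the proportions of patients with AEs and serious AEs, overall and by GBCA.
- **AE tables by SOC and PT:** show no p-values.

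Intervals adjusted for site with only 14 sites, and a short pre-named list of tests, are open to debate and are not needed for this correction.

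The change needs SAP wording, extra table columns and some programming, but no new data. The downside is wider tables and fewer headline p-values.
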